1.13 Adverse events

Adverse events and concomitant medications will be reviewed at every visit after V1A. Clinical photographs will be taken at each visit in order to monitor changes in the injection sites especially with regards to any suspicious lesions or adverse reactions locally. If suspicious lesions are detected then, the participant will be immediately assessed and managed by a consultant dermatologist and if found malignant then, the lesion will be excised as per GSTT guidelines. Physical examination and vital signs will be performed at every visit in order to assess any potential systemic adverse effects and treated as appropriate as per GSTT guidelines.

The Medicines for Human Use (Clinical Trials) Regulations 2004 and Amended Regulations 2006 gives the following definitions:

Adverse Event (AE): Any untoward medical occurrence in a subject to whom a medicinal product has been administered including occurrences which are not necessarily caused by or related to that product.

Adverse Reaction (AR): Any untoward and unintended response in a subject to an investigational medicinal product which is related to any dose administered to that subject.

Unexpected Adverse Reaction (UAR): An adverse reaction the nature and severity of which is not consistent with the information about the medicinal product in question set out in the Investigator's Brochure (IB) relating to the trial in question (for any other investigational product).

Serious Adverse Event (SAE), Serious Adverse Reaction (SAR) or Unexpected Serious Adverse Reaction (USAR): Any adverse event, adverse reaction or unexpected adverse reaction, respectively, that

- Results in death;
- Is life-threatening;

- Required hospitalisation or prolongation of existing hospitalisation;
- Results in persistent or significant disability or incapacity;
- Consists of a congenital anomaly or birth defect.

Suspected Unexpected Serious Adverse Reaction (SUSAR): Is defined as a serious adverse drug reaction, the nature and severity of which is not consistent with the information about the medicinal product in question set out in the IB relating to the trial in question, and which results in any of the outcomes set above.

Important Medical Events (IME) & Pregnancy: Although not a serious adverse event, any unplanned pregnancy will also be reported via the SAE reporting system (please see protocol version 4.0, section 9.4 for more details).

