1.13.1 Reporting responsibilities

Please see protocol version 4.0, section 9.4 for detailed reporting responsibilities.

Adverse Events and Serious Adverse Events that do not require reporting

The following will not require reporting although will be documented on the eCRF and will be included in the primary outcome.

Adverse event as a result of venesection and cannulation include:

- i) Mild bruising at site of needle puncture

Adverse event as a result of the skin biopsy include:

- i) Mild bruising at the site of the skin biopsy
- ii) Cutaneous skin infection requiring oral course of antibiotics
A small scar will result after each skin biopsy, resembling an old chickenpox scar.

All hospitalisations which are expected to take place as a result of disease progression including any planned elective surgeries will not be documented on the eCRF and will not be reported at the interim and the end-of-trial safety data analysis however they will be documented in the patient notes. This may include but not limited to:

- Skin
 - Skin infection
 - Review of a wound
 - Skin blisters/ erosions as part of EB wound
- Teeth

- Dental extractions/ abscess
- Hand
 - Hand surgery
 - De-gloving injury
 - Occupational Therapy review and splints
- Transfusions
- Overnight hospital stay for reviews
- Blood monitoring, routine blood tests
- Corneal abrasions
- Eye Infections
- Chronic eye problems due to EB
- Gastrointestinal problems
 - Dysphagia, oesophageal stricture and dilation
 - Gastrostomy insertion, leakage or blockage/ jejunal tube insertion leakage/ blockage
 - Regurgitation or vomiting as a result of oesophageal blisters/ stricture
 - NG tube insertion
 - Constipation
- Vertebral or other fractures
- IV bisphosphonates
- IV iron infusion
- Contractures requiring physiotherapy
- Hydrotherapy
- ENT
 - Tonsillitis
 - Otitis externa
 - Otitis media
- Pain
 - pain assessment for acute or chronic pain
 - pain from ongoing EB wounds
- Accidental injuries causing minor skin wounds

Thus, any hospitalisation that is not associated with the IMP will not be reported, unless the IMP results in a prolongation of existing hospitalisation. Unscheduled and/or emergency hospitalisations that are not expected due to the natural course of the disease will be reported via the sponsor's normal serious adverse event (SAE) reporting practice. AEs will be reviewed at each visit both from the patient's report as well as documentation from medical notes.

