2.5 Adverse event reporting (primary outcome)

Adverse events (AE), serious adverse events (SAE) and serious adverse reactions (SAR) as specified in the protocol will be reported to the data monitoring committee (DMC). Total number of events (AE, SAE, SUSAR and SARs) and number of patients experiencing at least one of each event (AE, SAE, SUSAR and SARs) will be tabulated (appendix - table 6). Individual listings of all adverse events will also be presented (appendix - table 7).

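### Read literally, two adjacent sentences in Protocol 9.5 and SAP 1.13.1 give opposite reporting rules for an unexpected hospitalisation judged unrelated to the product

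*SAP*

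**What the plan says.** SAP 1.13.1 sets apart a class of admissions: "All hospitalisations which are expected to take place as a result of disease progression including any planned elective surgeries". The SAP says that these "will not be documented on the eCRF and will not be reported at the interim and the end-of-trial safety data analysis"; they go only into the patient notes. A long, open-ended list of EB-related reasons for admission follows. Protocol 9.5 has the same list and the same exclusion from the interim and final safety analyses, although its paragraph does not itself repeat the SAP's statement about the eCRF.

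After the list, both documents carry the same two sentences. The first opens with 'Thus' and continues: "any hospitalisation that is not associated with the IMP will not be reported". Its only exception is a stay already under way that the product prolongs. The second begins: "Unscheduled and/or emergency hospitalisations that are not expected due to the natural course of the disease will be reported", and names the sponsor's normal SAE practice as the route.

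The definitions in SAP 1.13 bear on this. An AE is any untoward occurrence, "including occurrences which are not necessarily caused by or related to that product". One criterion that makes an event serious is "Required hospitalisation or prolongation of existing hospitalisation". SAP 2.5 makes these counts the primary outcome: "Total number of events (AE, SAE, SUSAR and SARs) and number of patients experiencing at least one of each event" will be tabulated, and Table 6 has separate rows for SAEs and SARs.

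**The concern.** The first sentence decides by causality and the second by expectedness. The two tests are not equivalent, and nothing in the section says which prevails. The admission caught between them is one that is neither part of EB nor attributed to the injected cells.

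This matters because SAEs are a named component of the primary outcome, separate from SARs. If the first sentence is applied as worded, an admission enters only once someone has attributed it to the product. In an open-label phase 1 study, that attribution is made by an investigator who knows that every participant was treated. Unexpected admissions first judged unrelated are events that a monitoring committee would want to see and judge for itself. The second participant's treatment also depends on there being no safety concern 4 weeks after the first participant's injections (Protocol 4.2, SAP 1.2).

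**Working it through.** **1. The two rules, case by case.** Admissions are classified by expectedness from the disease and by association with the product.

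| Admission | First sentence (causality) | Second sentence (expectedness) | Result |
|---|---|---|---|
| Expected, unrelated | Not reported | Does not apply | Consistent: not reported |
| Unexpected, related | Not exempted | Reported as SAE | Consistent: reported |
| Unexpected (unscheduled or emergency), unrelated | Not reported | Reported as SAE | **Conflict** |
| Expected type, but related | Not exempted, so reported by implication | Does not apply | Rests on the first sentence alone |

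Only the third row is contradictory. The fourth row matters for the fix, because there the first sentence does useful work.

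**2. Does other text settle it?** Protocol 9.4 requires all SAEs to be reported except those that the protocol exempts. That refers back to 9.5, so it does not rank the two sentences. The definitions in SAP 1.13 make an unrelated admission an SAE, since causality is not required and hospitalisation is a seriousness criterion. The causality scale in Table 7 has a category for events unlikely to be related, so listing of unrelated events is foreseen. Both points favour the second sentence, but neither document says that it governs.

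**3. What 'reported' means.** SAP 1.13.1 uses the word in two senses.
- Bruising and infection after venesection or biopsy do not require reporting, yet are on the eCRF and in the primary outcome. Here the word means onward safety reporting.
- Expected hospitalisations are not reported at the interim and final safety analyses. Here it means inclusion in the analysis.

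The first sentence concludes the second of these paragraphs, so the analysis sense is the more natural one. In that sense the SAE count changes with the rule followed. In the other sense, sponsor reporting changes and the tabulated count may not.

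**4. Size, as an illustration.** The plan's only interval (Protocol 10.1, SAP 1.14) is for 0 adverse reactions in 10 participants. The exact two-sided upper limit is 1 − 0.025^(1/10) = 0.3085, which matches the stated 31%.

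Suppose one participant has an unexpected, unrelated admission and there is no other SAE in the cohort. The same exact (Clopper-Pearson) method gives, for participants with an SAE:

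| n | First sentence followed | Second sentence followed |
|---|---|---|
| 10 | 0/10: 0–30.8% | 1/10: 0.3–44.5% |
| 5 | 0/5: 0–52.2% | 1/5: 0.5–71.6% |

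Each such participant moves the proportion by 1/10 = 10 percentage points at n = 10, or 1/5 = 20 points at n = 5.

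The documents give no rate for these admissions. Assume that each participant independently has probability p of at least one over 12 months. The chance that at least one occurs, so that the two rules give different SAE event counts, is 1 − (1 − p)^n:

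| Assumed p | n = 5 | n = 10 |
|---|---|---|
| 5% | 23% | 40% |
| 10% | 41% | 65% |
| 20% | 67% | 89% |
| 30% | 83% | 97% |

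The count of participants with an SAE differs with the same probability only if such an admission is the affected participant's sole SAE.

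**The case against.** The best defence is contextual. 'Thus' marks the first sentence as a summary of the list above it, and that list covers only expected or elective admissions. On that reading the second sentence is the specific rule for everything unscheduled outside the list, and there is no conflict. This is a fair reading and may be what was meant. It does not remove the problem, because the sentence says any hospitalisation and changes the test from expectedness to association with the product. Someone applying it as written would withhold the event.

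Four stronger inferences are tempting, and the documents do not support them.

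- A reader might infer that the primary-outcome count certainly changes. That depends on the sense of 'reported', and exclusion from the analysis is stated outright only for expected admissions.
- A reader might infer that, for hospitalisations, the SAE row of Table 6 reduces to the SAR row. That requires the second sentence to be disregarded.
- A reader might take 0/10 against 1/10 as an estimate of impact. It illustrates one event in a cohort with no other SAE, and the plan specifies counts for SAEs, not confidence intervals.
- A reader might conclude that the first sentence should be struck out. That would lose the exception for a stay prolonged by the product, and the implication that a listed type of admission is reported when it is associated with the product. The second sentence alone covers only unscheduled or emergency admissions.

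**Conclusion.** The point holds as a wording conflict in both documents, confined to unexpected admissions judged unrelated to the product. On a literal reading these are both excluded and included, and exclusion contradicts the SAP's own AE and SAE definitions. An effect on the SAE component of the primary outcome is likely but not certain: it rests on the first sentence using 'reported' as its own paragraph does. Otherwise the effect is on what reaches the sponsor.

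The size in this trial cannot be estimated, because no rate is given. With 5–10 participants, a single such admission as a participant's only SAE shifts the proportion with an SAE by 20 to 10 percentage points. AR, SAR and SUSAR counts are unaffected for a given causality assessment, and the stated 0–31% interval stands because it concerns adverse reactions. The correction should be made before safety data are tabulated, since it is cheap and removes an unblinded causality judgement as a filter on a primary-outcome component.

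**What to change.** Narrow the first sentence in Protocol 9.5 and SAP 1.13.1, using identical wording in both:

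- Exempt only those listed admissions that are expected from disease progression or planned electively **and** are not associated with the product.
- Keep the exception for an existing stay prolonged by the product.
- State that any other hospitalisation is recorded on the eCRF and counted as an SAE whatever its causality, and that relatedness decides only whether it is also an SAR.

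It would also help to say in each place whether 'reported' means reporting to the sponsor or inclusion in the safety analysis.

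The cost is a short edit to one paragraph in two documents, a few more SAE forms, and possibly a less favourable SAE count.

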1.14 Sample size

The aim of this phase 1 trial will be to recruit approximately 5–10 patients from GSTT EB clinical database. This is a rare disease with an incidence of 1 in 17,000 live births. As per our statistician's advice, even if no subjects experienced adverse reactions (i.e. 0% AR), a sample size of 10 would give a 95% confidence interval of 0% to 31% (exact CI from Stata®). A sample of 10 could still potentially provide reassurance that no more than 3 in 10 subjects should experience a given side-effect.

[figure not shown]
2 Data analysis plan

2.1 Recruitment of patients

A flow chart in accordance with the requirements of the CONSORT statement will be presented (Figure 2). This will include the number of eligible patients formally invited to participate in the study, number of patients agreeing to enter the trial, the number who proceed to skin biopsy/procurement, the number of patients receiving treatment (intradermal injections of gene-modified autologous fibroblasts) and the number of patients, with reasons, not proceeding to the next stage. It will also include the number of patients who complete each visit, and the number not completing (including those not completing due to withdrawal, loss to follow-up, and death).

A table of the number of patients consenting to enter the trial, the number who proceed to skin biopsy/procurement and the number of patients receiving treatment (intradermal injections of gene-modified autologous fibroblasts) will be presented by month (appendix - table 2). A table of visit completion status for each patient will be reported, including date enrolled (appendix - table 3).

Figure 2: Trial Flowchart

2.2 Baseline characteristics

The baseline characteristics of each patient will be reported, including demographics and clinical characteristics (appendix - table 4).

2.3 Treatment delivery

The number of patients who receive treatment will be reported (appendix - table 2).

Treatment related characteristics such as site of treatment and cell numbers injected will be summarised for each patient (appendix - table 5).

2.4 Loss to follow-up

The reasons for withdrawal from the trial will be reported (Figure 2).

All study participants will be included in all analyses unless they have withdrawn consent. For subjects who drop out rather than withdraw consent, a request will be made to use data collected prior to drop-out.

2.5 Adverse event reporting (primary outcome)

Adverse events (AE), serious adverse events (SAE) and serious adverse reactions (SAR) as specified in the protocol will be reported to the data monitoring committee (DMC). Total number of events (AE, SAE, SUSAR and SARs) and number of patients experiencing at least one of each event (AE, SAE, SUSAR and SARs) will be tabulated (appendix - table 6). Individual listings of all adverse events will also be presented (appendix - table 7).

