4.1.3 Primary endpoint

- Adverse events (AEs), Serious Adverse Events (SAEs), Adverse Reactions (ARs) and Serious Adverse Reactions (SARs) at each visit after screening over a 12-month follow-up period.

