8.1 Primary efficacy parameters

The primary efficacy of this phase 1 trial will be based on the safety of the administration of IMP in adults with RDEB, as analysed according to the incidence of Adverse events (AEs), Serious Adverse Events (SAEs), Adverse Reactions (ARs) and Serious Adverse Reactions (SARs) at each visit after screening over a 12-month follow-up period.

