1.12 Outcome measures

1.12.1 Primary outcome measures

Adverse events (AEs), Serious Adverse Events (SAEs), Adverse Reactions (ARs) and Serious Adverse Reactions (SARs) at each visit after screening over a 12-month follow-up period.

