¹Type of RDEB: *GS=Generalised severe, GI=Generalised intermediate, In=Inversa, Lo=Localised, PT=Pretibial, Pru=Pruriginosa, Cen=Centripetalis, BDNB=Bullous dermolysis of the new born.*

²*C7 IF microscopy: CD=Complete deficiency, PD=Partial deficiency, ND=No deficiency.*

³*C7 MII ± SE = Type VII collagen mean immunofluorescence intensity ± standard error*

⁴*AF ± SE = anchoring fibrils ± standard error*

Note: All baseline values are taken from visits 1A or 1B which are up to 6 months and 6 weeks prior to administration of IMP, respectively. With the exception of the ELISPOT values which are taken at visit 2 prior to administration of the IMP.

Table 5: Treatment related data per patient

Patient ID	Time from treatment of previous patient (days)	Date of treatment	Site of treatment	Cell numbers injected in Square 1 (x10 ⁶ cells in 0.25ml of 0.9% saline)	Cell numbers injected in Square 2 (x10 ⁶ cells in 0.25ml of 0.9% saline)	Cell numbers injected in Square 3 (x10 ⁶ cells in 0.25ml of 0.9% saline)
001	xx	dd/mm/yyyy		xx.x	xx.x	xx.x
002						
003						
004						
005						
006						
007						
008						
009						
010						

Table 6: Summary of adverse events and reactions, including SAEs

		Number of events nAE	Number of patients n
Overall			
Adverse events (AE)		xx	xx
Serious adverse events (SAE)		xx	xx
Suspected unexpected serious adverse reactions (SUSAR)		xx	xx
Serious adverse reactions (SAR)		xx	xx
Severity Grade¹			
1		xx	xx
2		xx	xx
3		xx	xx
4		xx	xx
5		xx	xx

NOTE: nAE = number of adverse events (or SAE/SUSAR/SAR); n =number of patients experiencing at least one event.

¹ **Severity grade:** 1=mild: awareness of signs or symptoms, but easily tolerated; 2=moderate: uncomfortable enough to cause interference with usual activity; 3=severe: incapacity with inability to work or do usual activity; 4=life-threatening; 5=death.

Table 7: Adverse events and reactions, including SAEs, per patient

Patient ID	Event	Days from treatment to onset	Start date dd/mm/yyyy	End date dd/mm/yyyy	Serious? ¹ Y/N	Severity Grade ² (1-5)	Causality ³	Outcome ⁴	Treatment (free text)	Medications received if any

¹**Serious:** yes/no. *NOTE: If yes, qualifies an AE/R as Serious (SAE/R)*

²**Severity grade:** 1=mild: awareness of signs or symptoms, but easily tolerated; 2=moderate: uncomfortable enough to cause interference with usual activity; 3=severe: incapacity with inability to work or do usual activity; 4=life-threatening; 5=death;

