³**Causality:** unlikely to be related / possibly related / probably related / definitely related. *NOTE: Causality of 'possibly' or greater qualifies an AE as an Adverse Reaction (AR).*

⁴**Outcome:** fully recovered/recovered with sequelae/no recovery/fatal

Table 8: Type VII collagen immunofluorescence microscopy and mean immunofluorescence intensity \pm standard error from skin biopsies per patient

Patient ID	C7 IF	Baseline		Week 2		Month 3		Month 12	
		Treated	Untreated	Treated	Untreated	Treated	Untreated	Treated	Untreated
001	Microscopy ¹								
	Intensity ²	xx.x \pm xx.x							
002	Microscopy ¹								
	Intensity ²	xx.x \pm xx.x							
003	Microscopy ¹								
	Intensity ²	xx.x \pm xx.x							
004	Microscopy ¹								
	Intensity ²	xx.x \pm xx.x							
005	Microscopy ¹								
	Intensity ²	xx.x \pm xx.x							
006	Microscopy ¹								
	Intensity ²	xx.x \pm xx.x							
007	Microscopy ¹								
	Intensity ²	xx.x \pm xx.x							
008	Microscopy ¹								
	Intensity ²	xx.x \pm xx.x							
009	Microscopy ¹								
	Intensity ²	xx.x \pm xx.x							
010	Microscopy ¹								
	Intensity ²	xx.x \pm xx.x							

Acronyms: IF = immunofluorescence.

¹C7 IF microscopy: CD=Complete deficiency, PD=Partial deficiency, ND=No deficiency.

²C7 MII \pm SE = Type VII collagen mean immunofluorescence intensity \pm standard error

Table 9: Morphology of anchoring fibrils at the dermal-epidermal junction (DEJ) by transmission electron microscopy (TEM): anchoring fibrils \pm standard error and integrity from skin biopsies per patient

Patient ID		Baseline	Week 2		Month 3		Month 12	
			Treated	Untreated	Treated	Untreated	Treated	Untreated
001	AF number ¹	xx.x \pm xx.x						
	Integrity							
002	AF number ¹	xx.x \pm xx.x						
	Integrity							
003	AF number ¹	xx.x \pm xx.x						
	Integrity							
004	AF number ¹	xx.x \pm xx.x						
	Integrity							
005	AF number ¹	xx.x \pm xx.x						
	Integrity							
006	AF number ¹	xx.x \pm xx.x						
	Integrity							
007	AF number ¹	xx.x \pm xx.x						
	Integrity							
008	AF number ¹	xx.x \pm xx.x						
	Integrity							
009	AF number ¹	xx.x \pm xx.x						
	Integrity							
010	AF number ¹	xx.x \pm xx.x						
	Integrity							

Acronyms: AF = anchoring fibrils.

¹AF \pm SE = anchoring fibrils \pm standard error.

Table 10: Vector copy number by quantitative polymerase chain reaction (qPCR) from skin biopsies per patient

Patient ID	Baseline	Week2		Month 3		Month 12	
		Treated	Untreated	Treated	Untreated	Treated	Untreated

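### The planned summary of the primary outcome (SAP 2.5, Table 6) has no row for adverse reactions, one of its four components

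*SAP*

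**What the plan says.** **Outcome definition.** SAP 1.12.1 lists AEs and SAEs together with "Adverse Reactions (ARs) and Serious Adverse Reactions (SARs) at each visit after screening over a 12-month follow-up period". Protocol 4.1.3 has the same four: "Adverse events (AEs), Serious Adverse Events (SAEs), Adverse Reactions (ARs) and Serious Adverse Reactions (SARs) at each visit after screening". Protocol 8.1 says how they are to be judged: "as analysed according to the incidence of Adverse events (AEs), Serious Adverse Events (SAEs), Adverse Reactions (ARs" and SARs.

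**Planned summary.** SAP 2.5, whose heading identifies it as the primary-outcome section, tabulates "Total number of events (AE, SAE, SUSAR and SARs) and number of patients experiencing at least one of each event". The shell in the SAP Appendix is titled "Table 6: Summary of adverse events and reactions, including SAEs". Its overall rows are AE, SAE, SUSAR and SAR, followed by severity grades 1 to 5. Its note defines the event count as "number of adverse events (or SAE/SUSAR/SAR".

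**Planned listing.** SAP 2.5 also requires Table 7, which lists every event by patient, with seriousness, severity and causality. A footnote to that table says that causality of possibly "or greater qualifies an AE as an Adverse Reaction (AR".

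**Precision.** SAP 1.14 (and Protocol 10.1) states that "even if no subjects experienced adverse reactions (i.e. 0% AR), a sample size of 10 would give a 95% confidence interval" of 0% to 31%.

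**The concern.** The endpoint and its planned summary do not list the same things. The text of SAP 2.5, the Table 6 rows and the Table 6 note agree with one another, and all three depart from the outcome definition. The title of Table 6 promises reactions, but the only reactions it counts are serious ones. Neither document explains the change.

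This matters because relatedness is central in a first study of an injected product. Protocol 9.1 expects local reactions such as mild pain, bruising, redness and itching. As described, these meet none of the seriousness criteria in SAP 1.13, so they fall outside the SAE, SAR and SUSAR rows. Table 6 would show them only within the AE row and the severity-grade rows, and neither separates related from unrelated events. The AE definition in SAP 1.13 takes in events not caused by the product. SAP 1.13.1 adds bruising from blood sampling and from biopsy to the primary outcome. Bruising from the injection and bruising from a needle puncture would be counted together.

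**Working it through.** **1. Components against rows.**

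| Category | Primary outcome (SAP 1.12.1, Protocol 4.1.3 and 8.1) | SAP 2.5 and Table 6 |
|---|---|---|
| AE | yes | yes |
| SAE | yes | yes |
| AR | yes | **no** |
| SAR | yes | yes |
| SUSAR | no | yes |

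Three of the four components have a row.

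**2. The plan's own figure.** Inputs are x = 0 patients with an AR, n = 10 and an exact two-sided 95% interval (SAP 1.14). With x = 0 the upper limit is 1 − 0.025^(1/n). For n = 10 it is 1 − 0.025^(1/10) = 0.3085, or 31% when rounded, so the figure reproduces. It refers to patients with at least one AR divided by patients, a proportion that has no cell in Table 6. At n = 5, the lower end of the stated 5–10 range, the same formula gives 1 − 0.025^(1/5) = 0.5218, or 52.2%.

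**3. Can the AR count be worked out from the other rows of Table 6?** Under the definitions and the Table 7 rule, every SAR is an AR and every AR is an AE. Hence:

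patients with a SAR ≤ patients with an AR ≤ patients with an AE.

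As an illustration, take 10 patients with AE = 10 and SAR = SUSAR = 0. Any AR count from 0 to 10 fits. The extremes are 0/10 (exact 95% CI 0–30.8%) and 10/10 (lower limit 0.025^(1/10) = 0.692, so 69.2–100%). The severity rows do not narrow this, because they carry no causality split.

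**4. Can it be worked out from Table 7?** Yes. Count the patients with at least one event whose causality is possibly, probably or definitely related. With at most 10 patients this is a short tally and leaves no uncertainty about the count.

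**5. What an AR row would allow.** It would supply x and n directly. Exact 95% intervals at n = 10 are 0–30.8% for 0/10, 0.3–44.5% for 1/10 and 6.7–65.2% for 3/10.

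**The case against.** The strongest reply is that ARs are not absent from the planned primary analysis. The same section that omits them from the summary requires Table 7, which has a causality column and the rule for deriving an AR. In a trial of 5–10 patients, individual listings are a main output, and the SAP relies on them for the secondary outcomes too. The 0/10 to 10/10 spread in step 3 arises only if Table 6 is read without Table 7. All of this stands, and it limits the point to a missing summary row. It does not remove the point: SAP 2.5 plans both a summary and a listing, the summary leaves out a named component, and the AR rule appears only in a footnote to the listing.

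A second reply is that the 0–31% interval is an illustration. The recruitment target is a range, the text cites the rarity of the disease, and its conclusion concerns any given side-effect and not all ARs pooled. That also stands. A reader might infer that the sample size was derived from the AR proportion, but the documents do not say so. They show only that the one precision figure is expressed in terms of ARs.

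A third reply is that neither document plans a confidence interval for any observed result, so adding one is a preference. That is right, and the gap closes without one.

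**Conclusion.** The point holds as a gap in the planned summary of the primary outcome: one of four components has no row, and it is the one to which the only precision statement refers. It is worth correcting before analysis, but it is modest in size. It rests on reading SAP 2.5 and the Table 6 shell as the complete list of summary categories. The agreement of text, rows and note supports that reading.

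Three stronger readings are tempting and not supported:

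- **That ARs go unrecorded or unanalysed.** Table 7 captures them and says how to identify them.
- **That mild reactions would be counted only in the AE row.** They would also appear in the severity-grade rows, though still not separated by cause.
- **That Table 6 should at the same time be limited to onset from Day 0, with injected participants as the denominator.** The tissue-procurement biopsy takes place at V1B, before Day 0, and SAP 1.13.1 includes biopsy bruising and infection in the primary outcome. SAP 2.4 and Protocol 10.2 keep all study participants in all analyses unless consent is withdrawn. The AE definition in SAP 1.13, which refers to people given the product, may point the other way. Those passages need reconciling separately, and adding an AR row does not depend on the result.

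**What to change.** 1. In SAP 2.5, add AR to the categories tabulated, both as events and as patients with at least one.
2. In Table 6, add an AR row defined by the existing Table 7 rule (causality possibly or greater), and extend the note to match. Keep SUSAR as an additional row.
3. Show the patient count as n/N and state what N is, in line with whatever population the SAP settles on.
4. Optionally, give an exact 95% interval for the AR proportion, matching the method in SAP 1.14. It would be descriptive and consistent with the decision not to test hypotheses.

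The cost is one phrase in the SAP and one row in a table shell. Causality is already recorded for each event in Table 7, so no new data, visits or patients are needed.
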